12.1 Serious Adverse Events

A serious adverse event (SAE) is defined as any untoward medical occurrence that:

- Results in death;
- Is life-threatening (i.e., an event in which the subject was at risk of death at the time of
 the event; it does not refer to an event which hypothetically might have caused death ifit
 were more severe).
- Requires inpatient hospitalization or prolongation of existing hospitalization.
- Results in persistent or significant disability/incapacity.
- Results in a congenital anomaly/birth defect.
- In the opinion of the investigator, is an important medical event that may not be immediately life-threatening or result in death or hospitalization but may jeopardize the subject or may require intervention to prevent one of the other outcomes listed in the definition above, or that may be considered serious. Examples of such events are intensive treatment in an emergency department or at home for allergic bronchospasm; blood dyscrasias or convulsions that do not result in hospitalization; or development of drug dependency or drug abuse.

12.2 Study Drug Relationship

The Principal Investigator and the Study Sponsor are responsible for assessing the causal relationship between any events and the study treatment (table 3). Additionally, the investigator is responsible for providing appropriate treatment for the event and for adequately following the event until resolution. The principal investigator and study sponsor should determine the study drug relationship using the following definitions:

Table 4. Criteria fo	r attributing relationship of AE and SAE to studydrug					
Unrelated	No temporal association to study product.					
	An alternate etiology has been established.					
	The event does not follow the known pattern of response to study product.					
	The event does not reappear or worsen with re-challenge.					
Probably not	No temporal association to study product.					
related / remote	Event could readily be produced by clinical state, environmental or other					
	interventions.					
	The event does not follow the known pattern of response to study product.					
	The event does not reappear or worsen with re-challenge.					
Possibly related	Reasonable temporal relationship to study product.					
	The event is not readily produced by clinical state, environmental, or other					
	interventions.					
	The event follows a known pattern of response to the study product or as yet					
D 1 11 1 1 1	unknown pattern of response.					
Probably related	There is a reasonable temporal association with the study product.					
	The event is not readily produced by clinical state, environmental, or other					
	interventions.					
	The event follows a known pattern of response to the study product.					
Definitely related	The event decreases with de-challenge.					
Definitely related	There is a reasonable temporal relationship to the study product.					
	The event is not readily produced by clinical state, environmental, or other interventions					
	intervention.					
	The event follows a known pattern of response to the study product. The event decreases with de-challenge and recurs with re-challenge.					
	The event decreases with de-challenge and recurs with re-challenge.					

Temporal sequence is defined as an association between the suspect drug and the observed reaction or event in which the suspect drug was present prior to the reaction or event as defined by history or blood level of drug.

Study drug(s) includes the drug(s) under evaluation, the reference drug(s), placebo, or any other drug(s) required by the protocol.

Severity of an adverse event will be defined from the qualitative assessment of the degree of intensity of the event as determined by the principal investigator or as reported to him/her by the subject.

12.3 Guidelines for Serious Adverse Events Reporting

Serious adverse events are defined by the FDA as any untoward medical occurrences that result in death, are life-threatening, require or prolong hospitalization, cause persistent or significant disability or incapacity, result in congenital anomalies or birth defects, or are other conditions which in the opinion of the investigator represents significant hazards.

Any and all serious adverse events relating to the acquisition of blood samples, and the application of the study cream, will be reported in writing to the chair of the IRB. The written report of the serious adverse event (e.g., death or life-threatening adverse event) will be sent within 5 days if the serious adverse event is unexpected and possibly, probably, or definitely related to participation in the study. In the event that an adverse event or deviation occurs that could present an immediate or urgent danger to subjects, the IRB chair will be contacted immediately.

All serious adverse events and unexpected non-serious adverse events relating to the acquisition of blood will be summarized and reported at the time of the continuing review.

> PI: [name] Version 5

Vaso-occlusive crisis occurs frequently and at unpredictable intervals in subjects with sickle cell disease, often requiring hospitalization. These events are expected and they will be summarized and reported at the time of the continuing review.

13. Data and Safety Monitoring Plan

The PI will assemble an independent Data Safety Monitoring Board, composed by 4 individuals appointed from within and outside the institution to ensure safe and effective conduct of the trial. The DSMB may recommend early termination of the study for considerations of safety and efficacy. A progress report will be forwarded to the DSMB at these times. The DSMB will meet with the Principal Investigator annually to perform the following activities:

- a. Assess participant safety, including:
 - i. All protocol deviations and adverse events
 - ii. All scientific or therapeutic developments that may have an impact on the safety of the participants or the ethics of the study.
 - iii. Benefit/risk ratio of procedures and participant burden
- b. Evaluate trial progress, including:
 - i. Quality, accuracy, and timeliness of collected data and statistical analysis
 - ii. Selection, recruitment, and retention of participants
 - iii. Confidentiality of trial data
 - iv. Efficacy of the study intervention
- c. Performance of clinical research sites, including:
 - i. Performance of clinical research pharmacy and the core lab
 - ii. Adherence to protocol requirements
- d. Make recommendations to the IRB and investigators, including:
 - i. Continuation or conclusion of the trial
 - ii. Amendments to the study protocol and consent forms

Safety Monitoring:

Principal Investigator: Accrual and safety data will be monitored by the PI. The protocol will be continuously evaluated for any unusual or unpredicted complications with the sodium nitrite cream.

Accrual and safety data will be monitored and reviewed annually by the Institutional Review Board (IRB). Prior to implementation of this study, the protocol and the proposed informed consent and assent documents will be reviewed and approved by the properly constituted Institutional Review Board (IRB) operating according to the 45 CFR 46 Code of Federal regulations. This committee must approve all amendments to the protocol or informed consent, and conduct continuing annual review so long as the protocol is open to accrual, open forfollow up of subjects or open for data analysis and sharing.

Data Management. The PI will be responsible for overseeing entry of data into an in-house password protected electronic system (RedCap web application) and ensuring data accuracy, consistency and timeliness. The principal investigator, associate investigators, research nurses and/or a data manager will assist with the data management efforts. RedCap will be the main electronic system for data collection while paper CRFs will serve as a backup. Data will be entered into RedCap in real time whenever feasible. However,data can also be abstracted from Clinical Center progress notes as well as intake form and the other paper based case report forms. For data not entered in real time, source documents will be kept in the subject binder and entered at a later time. Date of entry will be automatically recorded. Data will be stored in locked cabinets and in a password protected database until it is no longer of scientific value.

32

[figure not shown]
PI: [name]

Loss or Destruction of Data: Should we become aware that a major breech in our plan to protect patient confidentiality and trial data has occurred, the IRB will be notified.

	Screening€	Baseline	Run-in				Double-B	linded Stu	dy Treatn	nent Phase	2			EOS
Visit Number	0	1	2	3-4	5-6	7-8	9-10	11-12	13-14	15-16	17-18	19-20	21-22	23
Week on Study Intervention		Week ~-2	Week ~-1	Week 1	Week 2	Week 3	Week 4	Week 5	Week 6	Week 7	Week 8	Week 9	Week 10	Week
Assessment Window	-	-	-	± 3 d	± 3 d	± 3 d	± 3 d	± 3 d	± 3 d	± 3 d	± 3 d	± 3 d	± 3 d	± 3 d
Study Procedure		•						 						
Informed Consent	х													
Basic Contact Info	х													
Demographics	х													
Medical History	х													
Beck Depression Inventory		x												x
ASCQ-Me		x												x
PROMIS		x												x
Brief Pain Inventory		x	x											x
Concomitant Medications	х	x		xx	xx	xx	xx	xx	xx	хх	xx	xx	xx	x
Vital Signs	x	x	x	xx	xx	xx	xx	xx	xx	xx	xx	xx	хх	x
Baseline Physical Exam		x												
Non-Baseline Physical Examination	x			v3				x						x
MetHb	х			v3				x				x		
G6PD	χa													
Hb Electrophoresis	x ^b													x
Baseline and EOS Labs		х												x
Monitoring Labs				x				X				х		
Research Labs (3 tubes) Saliva for DNA		x												x
Analysis		x												
Urine Pregnancy Test*		x						x						x
Randomization				v3										
Application of Cream				xx	xx	xx	xx	xx	xx	xx	xx	xx	xx	
Wound Care		x	x	xx	xx	xx	xx	xx	xx	xx	xx	xx	xx	x
Ulcer History	х													
Ulcer Assessment	x	x	x	xx	xx	xx	xx	xx	xx	xx	xx	xx	xx	x
Ulcer Photography		x	x	x					v13					x
Ulcer Biopsy			x											
Ulcer Microbiome			v2											x
Dose Modification									v13					

^{*:} For women of childbearing potential only

xx: Twice per week assessment

a: If the subject had documented normal G6PD and metHb lab results, then no need to repeat

b: Only if no results available within 3 months

€: Screening and baseline can be combined into one visit

After the first three subjects have completed the study, if there are no significant side effects, especially significant changes in BP, patients will be offered the option of applying the second weekly dose of the cream at home, by themselves or by a home health nurse. Dose modification and ulcer photography for visit 13 can be done anytime between visit 11-15.

34

15. References Cited

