7.1 Monitoring of Subjects and Criteria for Withdrawalof Subjects

Monitoring: The safety of topical sodium nitrite will be closely monitored. Vital signs will be obtained before application and post-application at hours 1, 2, 3, 4, 5. If no decrease in systolic blood pressure is detected (clinically significant hypotension: see Section 7.1), patients will be discharged home.

The primary expected toxicity is low grade, asymptomatic methemoglobinemia. Therefore, a blood sample for methemoglobin safety measurement will be obtained after the first application, then weekly.

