7.2 Stopping Rules

The study medication will be stopped if the subject experiences healing of the ulcer.

Subjects will be removed from therapy should one or more of the following occur:

- If any methemoglobin reading is >7.5%, the research study cream will be discontinued.
- Investigator or patient considers discontinuation of the study to be in the patient's best interest.
- Clinically significant hypotension (decrease in the systolic BP >20mmHg from the baseline systolic BP and of 10mmHg from the baseline diastolic BP application, and symptomatic dizziness, tachycardia, or hypoxia as per the judgment of the PI).
 - A dose will be skipped if the subject has a systolic blood pressure of ≤80mmHg and/or a diastolic blood pressure of ≤50mmHg, once the blood pressure has been checked with a repeat blood pressure check. If three doses are skipped in a row for this reason, the subject will be removed from therapy.
- Sustained pulse oxygen saturation below 85% for >15 minutes while on supplemental oxygen (up to 4L by NC).

- Increased ulcer pain requiring increased opioid use by 50%.
- Development of osteomyelitis or other systemic infection while on therapy.
- Lack of compliance, as measured by missing more than two sequential cream applications and/or at the PI's discretion.

Rules for Stopping the Study:

- Occurrence of severe toxicities:
 - Three subjects requiring sodium nitrite cream discontinuation
 - Death while on protocol, if it is attributable to the sodium nitrite cream

8. **Analysis of the Study**

We will first review and summarize data using descriptive summaries and graphical analyses to ensure recorded values are within appropriate ranges, in order to check for outliers and abnormal values. We will explore the success of randomization by comparing groups on potential confounding variables, and will include variables that are not equally distributed between groups in multivariable models. For primary analyses, we will adhere to the intent-totreat analysis principle that assigns groups as randomized as opposed to actually treated. For sensitivity analyses, we will conduct as-treated analysis and use incomplete data as well after imputation of missing data due to early dropouts; imputation methods such as last-observationcarried-forward or MCMC will be conducted and results from thereof will be compared.

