PI: [name] Version 5 62/077,622, filed on November 10, 2014, entitled "TOPICAL SODIUM NITRITE FORMULATION," and PCT Patent Application No. PCT/US2015/060015, filed on November 10, 2015, entitled "TOPICAL SODIUM NITRITE FORMULATION," has six inventors: [name], [name], [name], [name], [name], and [name], who were all NIH employees at the time of invention.

- Or. [name] is presently employed on the faculty of the University of Pittsburgh.
- oDr. [name] is presently employed on the faculty of the Albert Einstein College of Medicine.

12 Adverse Events Reporting

The Principal Investigator (or a physician member of the research team) and the study coordinator will assess each participant for any new or continuing adverse events. An adverse event is defined as any untoward medical occurrence in a subject of a clinical investigation that involves the administration of a pharmaceutical product. The event need not to have a causal relationship with the treatment. This includes any events that are not seen at baseline or, if present at baseline, have worsened in severity. These adverse events will only be collected during study treatment time. The severity and drug relationship will be determined, and any management required will be recorded. The investigator will review the clinical laboratory test results in a timely fashion. Only those results qualifying as adverse events, as defined above, will be recorded as an adverse event.

Table 2. Expected Adverse Events Possibly Related to Study Drug						
Severe stinging and burning sensation, requiring an increase in narcotic use.						
Peripheral vasodilation with hypotension (BP below 85/50, or symptomatic						
dizziness, tachycardia, or hypoxia as per the judgment of the PI)						
Methemoglobinemia >7.5%						

Acute chest syndrome Angioedema Angioedema Aplastic crisis Aplastic crisis/anemia Aplastic crisis/anemia Appendicitis Bone Infarction Cardiomegaly Cerebrovascular accident Cholecystitis, hepatic sequestration Cranial nerve palsy Decreased kidney function Decreased lung function Pever Renal Insufficiency/albuminuria Headache Hematuria Hematuria Reticulocytosis (10%-20%) Hemiplegia Hemolysis Hepatosplenomegaly Hyperplastic bone marrow Hyposthenuria Increase Jaundice Metabolic acidosis	Table 3. Expected Adverse Events Re	elated to Sickle Cell Disease

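### Table 2 lists the cream's main feared toxicities as expected at any severity, so a serious, related case has no fixed reporting deadline and no described route to the DSMB before its annual meeting

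*Combined protocol and SAP*

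**What the plan says.** Section 12.3 requires serious events relating to the study cream to be reported in writing to the IRB chair. A time limit is attached to only some of them: the report "will be sent within 5 days if the serious adverse event is unexpected and possibly, probably, or definitely related to participation in the study". Both conditions must be met. A separate sentence requires the chair to be contacted at once about an event that could put subjects in urgent danger. Vaso-occlusive crises are called expected and left to the continuing-review summary.

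What counts as expected is listed in Section 12. "Table 2. Expected Adverse Events Possibly Related to Study Drug" has three entries: severe stinging or burning that needs more narcotic; an entry that begins "Peripheral vasodilation with hypotension (BP below 85/50, or symptomatic"; and "Methemoglobinemia >7.5" per cent. None carries a grade or an upper severity limit. Table 3 adds events attributed to sickle cell disease.

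Section 7.1 describes a much milder expectation: "The primary expected toxicity is low grade, asymptomatic methemoglobinemia".

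Section 7.2 stops the study for severe toxicity on "Three subjects requiring sodium nitrite cream discontinuation". In Section 13, "The DSMB will meet with the Principal Investigator annually".

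**The concern.** The purpose of a short reporting clock is to get new safety information quickly to people outside the treating team. Here the toxicities that the investigators most fear from this cream are on the list that takes an event off the clock, however severe the case. Phase 1 (Sections 1 and 2.4) had no serious event and no grade 3–4 event, so a serious methemoglobinemia or hypotension would be the first seen with this preparation. Section 2.4.2 says the placebo comparison is meant to settle the blood-pressure question, and Section 8.1 makes tolerability and adverse effects the primary endpoint.

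The stopping rule adds to this. It counts discontinuations of active cream, but Section 5.2 names only the pharmacist as unblinded. Section 5.3 plans two sites, and no text says who adds up the count across them. The medical monitor and the DSMB are the natural parties to do so, and neither has a stated time by which it must be told.

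**Working it through.** The point rests on reporting rules, so the check is a side-by-side reading followed by one piece of context arithmetic. The plan states no figure to reproduce here.

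**Step 1. What is listed as expected, against the plan's own expectation and its removal criteria.**

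| Event | Table 2 (expected) | Section 7.1 and phase 1 (Section 2.4) | Sections 5.4 and 7.2 |
|---|---|---|---|
| Methemoglobinemia | Above 7.5%, no ceiling | Mild and symptom-free; phase 1 maximum 4.1% | Dose-limiting above 7% (5.4); cream stopped above 7.5% (7.2) |
| Hypotension | Below 85/50, or symptoms; no floor | Phase 1: grade 1 diastolic readings under 50 mmHg, 16 times in 4 participants, all resolved spontaneously | Dose skipped at systolic 80 or less and/or diastolic 50 or less; removal after three skips in a row, or on a symptomatic fall from baseline (7.2) |
| Stinging or burning | Severe, needing more narcotic | Phase 1: brief stinging in three subjects, no intervention | Pain needing 50% more opioid (5.4 and 7.2) |

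In every row Table 2 covers cases well beyond anything seen in phase 1. The methemoglobin and blood-pressure figures also differ between sections.

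**Step 2. Follow one serious case of a Table 2 event, judged at least possibly related, through each route in the text.**

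1. Five-day report (12.3): needs unexpected and related. A listed event meets the second condition and fails the first, so no 5-day deadline applies.
2. General written report to the IRB chair (12.3): applies, with no deadline.
3. Immediate contact with the IRB chair (12.3): applies only if the event is judged an urgent danger.
4. Medical monitor (5.2): may ask for unblinding after a serious event or dose-limiting toxicity. No duty or time to notify the monitor is stated.
5. Sponsor (12.2): shares the causality assessment, with no reporting time.
6. DSMB (13): annual meeting. A progress report is mentioned, but its timing is not defined and no expedited route is described.
7. IRB periodic review (13): annual.

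The IRB chair must therefore be told, but by no stated date unless route 3 is triggered. The DSMB's first described contact is its annual meeting.

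**Step 3. How much exposure fits into that interval.** Inputs: 1–2 subjects a month and 50 randomized at 1:1 (Section 5.2); a 10-week course.

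- Enrolled between annual meetings: 1 × 12 = 12 to 2 × 12 = 24.
- Share of the trial: 12/50 = 24% to 24/50 = 48%.
- On active cream: about 12/2 = 6 to 24/2 = 12.
- Consecutive courses in a year: 52/10 = 5.2.

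**The case against.** Four arguments on the other side carry weight.

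- **The case does leave the site.** A reader might infer that a serious, related case need not be seen outside the site until a yearly review. Section 12.3 does not support that. It asks for a written report to the IRB chair on every serious event relating to the cream, expected or not, and for immediate contact in urgent danger, which a life-threatening methemoglobinemia could well trigger. What is missing is a deadline and a described DSMB route.
- **The infections.** Section 7.2 also removes a subject for "Development of osteomyelitis or other systemic infection while on therapy", and Table 3 lists osteomyelitis, sepsis and meningitis as expected. It is tempting to count these too. But under Section 12.2 an event is possibly related only if the patient's clinical state does not readily produce it. These infections would often fail on relatedness before expectedness mattered. The point rests on Table 2.
- **The stopping rule.** One might infer that the reporting rule delays exactly the events that the stopping rule counts. It does not. Section 7.2 counts discontinuations, and many are not serious under Section 12.1. A symptom-free methemoglobin reading above 7.5%, or a 50% rise in opioid use, meets no seriousness criterion by itself. Removing the expectedness condition would not bring those in, so they need a separate notification.
- **Expected could be read with severity in mind.** Section 12.3 neither defines unexpected nor cites Tables 2 and 3, and Section 7.1 would let an investigator treat a serious, symptomatic case as unexpected. That reading is open, but Table 2 sits in the same section, carries the word expected in its title and sets no limit. Two sites could apply the rule differently.

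It is also true that the principal investigator monitors safety continuously (Section 13), that removing an individual subject does not wait for any outside report, and that a DSMB charter or other procedures not included here may set timelines.

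**Conclusion.** The point holds in this form: a serious, cream-related case of a Table 2 toxicity has no fixed reporting deadline unless it is judged an urgent danger, and no described route to the DSMB before its annual meeting. Table 2 also conflicts with Section 7.1 and goes well beyond the phase 1 experience.

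The size is a window, not a risk. Between meetings 12–24 subjects could be enrolled, about 6–12 of them on active cream. The documents give no rate for serious events on this cream, so no expected number of delayed reports can be calculated.

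The conclusion assumes that Tables 2 and 3 define what is expected, that accrual runs as planned, and that no separate charter or procedure already sets shorter times. If one does, the remaining task is to cite it in Sections 12.3 and 13. The change is worth making because safety is the primary question and only wording is involved.

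**What to change.** - Amend Section 12.3 so that any serious event at least possibly related to the cream is reported to the IRB within the same 5 days, with a copy to the medical monitor and the DSMB, whether or not it appears in Table 2 or 3.
- Within the same time, notify the medical monitor and DSMB of each discontinuation for toxicity that counts towards the three-subject rule, serious or not. Leave out removals for non-compliance, patient or investigator preference without toxicity, and healing. Section 5.2 allows for 20% dropout (0.20 × 50 = 10 subjects), so expediting every removal would add reports that carry no safety signal.
- Keep vaso-occlusive crisis in the continuing-review summary.
- Reconcile Table 2 with Section 7.1, and reconcile the methemoglobin figures (7% in Section 5.4, 7.5% in Section 7.2 and Table 2) and the blood-pressure figures (80/50 in Section 7.2, 85/50 in Table 2). Which values should stand is for the investigators to decide.

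The cost is protocol wording and a small number of extra expedited reports. Design, sample size and analysis are unaffected.
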